6 STUDY INTERVENTION DISCONTINUATION AND PARTICIPANT DISCONTINUATION/WITHDRAWAL

6.1 DISCONTINUATION OF STUDY INTERVENTION

The intervention will be discontinued if participants request it or if the remote connection fails due to technology problems. Training will be discontinued also if there is any sign of adverse or iatrogenic effect.

6.2 PARTICIPANT DISCONTINUATION/WITHDRAWAL FROM THE STUDY

Participants are free to withdraw from participation in the study at any time upon request. An investigator may discontinue or withdraw a participant from the study for the following reasons:

- Non-compliance to study protocol
- If any clinical adverse event (AE), laboratory abnormality, or other medical condition or situation occurs such that continued participation in the study would not be in the best interest of the participant

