5 STUDY INTERVENTION

5.1 STUDY INTERVENTION(S) ADMINISTRATION

5.1.1 STUDY INTERVENTION DESCRIPTION

All visits will be conducted by two individuals, a researcher (who is also certified as a CPS technician) and a technician. Following baseline activities, the researcher will inform the participant of their random assignment to a condition, either installation with a certified technician via interactive virtual presence or installation via the traditional live technician interaction. In cases where there is more than one restraint in the vehicle, the researcher will use a random number generator to select one of the restraints as the target for the research.

Those parents randomly assigned to the interactive virtual presence condition will be instructed how to connect to the interactive virtual presence program using their personal smartphone. Participants will connect to the interactive virtual presence program, view a brief online instructional video on using it, and then connect remotely to a certified technician.

Ensuring ecological validity and pragmatic trial practice, the researcher and local technician will purposely “stay away” through the remote installation process, allowing the parent and remote technician to engage via interactive virtual presence to install the restraint correctly in the vehicle. Remote technicians will guide the interaction following standard Safe Kids Worldwide practice for live in-person installations and participants will physically install and adjust the restraint into their own vehicle.

Those parents assigned to the control condition, installation by a live technician, will engage in standard procedures at Safe Kids Worldwide car seat checks to install the target restraint into the vehicle. The live technician will not be the same individual as the researcher, although they will both be present at the same location during the research protocol.

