7 STUDY ASSESSMENTS AND PROCEDURES

7.1 STUDY ASSESSMENTS

We will consider two primary outcomes, both derived from inspections of child restraint installations using objective coding sheets: (a) total number of inspection points that are correctly installed, translated into a percentage to account for different points for different (e.g., rear-facing vs forward-facing; seat belt vs LATCH) installations, and (b) dichotomous measure of whether the restraint was installed correctly vs. not correctly. Examples of inspection points include whether tether straps are twisted, whether the seat moves more than 1 inch to the left/right, whether seat belts are routed through the correct belt pathway, and whether the carrying handle is in the correct position.

Both outcomes will be collected at four time points: at baseline prior to any intervention, at post, immediately following the initial installation in both groups, at the start of the follow-up visit following 4 months of no active intervention by the research team, and at follow-up after parent installation without technician assistance.

We also will consider results from a brief knowledge questionnaire, which was adopted from an existing instrument. Secondary and covariate measures considered will include demographic traits of the participant (e.g., gender, race, ethnicity, SES, research site) and restraint (e.g., forward vs rear facing, LATCH vs seat belt installation), attitudes and beliefs about child restraints, perceived efficacy of the interventions, and reported behaviors using restraints.

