8.3 STATISTICAL ANALYSES

Descriptive Statistics and Covariates. Descriptive statistics for participants randomized to each intervention will be summarized for each outcome using measures of central tendency (mean, median, proportion) and variability (variance, standard deviation, range). Several covariates may impact the relation between the intervention and the outcome measures of interest, and they will be similarly summarized descriptively. These include demographics (age, gender, target child birth order, race, ethnicity, SES); study site; type of vehicle; type of child restraint (including forward- vs. rear-facing); and attitudes, beliefs, and behaviors surrounding child restraints. Because parents will be randomized to the interventions, we expect covariates to be balanced across intervention groups. We will assess balance across intervention groups and utilize covariates in the primary analyses if appropriate. We also will estimate interaction effects to determine whether the intervention is more or less effective among particular subgroups that are adequately represented in the sample.

Primary Analyses. We have three specific aims. Specific Aim 1 is to identify how accurate parents are at installing child restraints using instructions from technicians via interactive virtual presence. We expect to find over 90% or greater of restraints are installed correctly in all respects. We also will investigate individual components of installation and expect over 90% of components, across participants, will be installed correctly. 95% confidence intervals for all of these outcomes will be calculated and presented graphically as a Forrest Plot with a reference line set at 0.90. Identical analyses will be conducted for the group randomized to in-person installation.

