Specific Aim 2 will test whether child restraint installation by interactive virtual presence achieves installation accuracy at a rate not inferior to installation with a live technician. Two models will be computed, one with a measure of installation accuracy (proportion of all child restraint installation components performed correctly) as the dependent variable and the other with the dichotomous outcome of correct (100% correct installation across all components) vs. incorrect installation (<100% correct installation) as the dependent variable. Assuming that improvement is reflected by a positive value (that is, a higher post-training value is better), our primary model, based upon installation accuracy, is:

$$H_0: \Delta_{LIVE} - \Delta_{IVP} \geq \delta \text{ vs. } H_A: \Delta_{LIVE} - \Delta_{IVP} < \delta$$

where δ is the non-inferiority margin and IVP stands for interactive virtual presence. We will assume a non-inferiority margin of 0.025 for the primary analysis (see power analysis) and perform Analysis of

Covariance (ANCOVA) to determine if the difference of mean installation accuracy scores between the two groups falls below the non-inferiority margin of 0.025, after adjustment for the baseline measure of installation accuracy and other relevant covariates. Based on previous work, we do not anticipate non-normality of the continuous outcome variable of installation accuracy. However, we will assess normality using graphical techniques (normal probability plot, histograms) prior to analysis and will transform outcomes if appropriate. The one-sided non-inferiority test will be conducted using a Type I error of 0.025.

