9.1.5 PROTOCOL DEVIATIONS

A protocol deviation is any noncompliance with the clinical trial protocol requirements. The noncompliance may be either on the part of the participant, the investigator, or the study site staff. As a result of deviations, corrective actions will be developed and implemented.

These practices are consistent with ICH GCP:

- 4.5 Compliance with Protocol, sections 4.5.1, 4.5.2, and 4.5.3
- 5.1 Quality Assurance and Quality Control, section 5.1.1
- 5.20 Noncompliance, sections 5.20.1, and 5.20.2.

It is the responsibility of the Principal Investigator to use continuous vigilance to identify and report deviations within 10 working days of identification of the protocol deviation. Protocol deviations must be sent to the reviewing Institutional Review Board (IRB) per their policies. The Principal Investigator is responsible for knowing and adhering to the reviewing IRB requirements.

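### Does allowing investigators to withdraw participants for non-compliance, with no analysis set named in 8.3, undermine the non-inferiority test?

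*Combined protocol and SAP*

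**What the plan says.** Section 6.2 covers withdrawal by the participant and by the investigator. On the latter it says "An investigator may discontinue or withdraw a participant from the study for the following reasons", and lists "Non-compliance to study protocol" together with a clinical-event reason. It does not say whether outcome assessment continues afterwards or whether scores already collected are kept.

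Section 9.1.5 is broad: "A protocol deviation is any noncompliance with the clinical trial protocol requirements". It provides for corrective action and reporting, not for handling data.

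Section 6.1 deals with stopping the intervention, not leaving the study: "The intervention will be discontinued if participants request it or if the remote connection fails due to technology problems". Section 6.3 defines loss to follow-up and attaches no analysis consequence.

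Under 5.1.1, after baseline activities, "the researcher will inform the participant of their random assignment to a condition". Section 7.1 places the next inspection "at post, immediately following the initial installation in both groups".

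Section 8.3 opens with "Descriptive statistics for participants randomized to each intervention will be summarized for each outcome". For Aim 2 it specifies an ANCOVA, adjusted for baseline accuracy, to establish whether "the difference of mean installation accuracy scores between the two groups falls below the non-inferiority margin of 0.025". Aim 3 applies the same strategy to six further models. No intention-to-treat or per-protocol set, missing-data method or related sensitivity analysis is named.

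**The concern.** The worry is selective loss. The assignment is announced on site, and no blinding is described, so a withdrawal for non-compliance could be decided by someone who knows the arm. The remote arm has more steps that can go wrong, and connection failure can occur only there. A participant withdrawn between the announcement and the post inspection would have no post score and could not enter the Aim 2 ANCOVA. If such participants were mostly weak installers in the remote arm, those remaining would flatter remote assistance, and in a non-inferiority test that favours the claim being tested.

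Five of the six Aim 3 models use data from the 4-month visit, where ordinary attrition adds to the losses. With no written analysis set, an analyst could in principle choose after seeing the data. The margin is a quarter of the assumed SD (0.025 against 0.10) and the trial is large, so a small bias could matter.

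**Working it through.** **Inputs from 8.2 and 8.3.** SD 0.10; margin 0.025; one-sided alpha 0.025; total N 1476; 10% attrition; 664 per group in the power table. The documents give no number of withdrawals and no scores for withdrawn participants, so every count *k* and shortfall *s* below is an assumption.

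**The plan's own figures.** 2 × 664 = 1328, and 1328/0.9 = 1475.6, which rounds up to 1476, or 738 randomised per arm. With SE = 0.10 × √(2/664) = 0.00549, power at no true difference is Φ(0.025/0.00549 − 1.96) = 0.995. At a true difference of 0.01 it is Φ(0.015/0.00549 − 1.96) = 0.780. Both match the table. The 664 that 8.2 calls randomised is the number left after attrition; this is a slip of label that changes no figure.

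**Bias needed to double the error rate.** At 738 per arm, SE = 0.10 × √(2/738) = 0.00521. Moving from 2.5% to 5% needs a bias of (1.960 − 1.645) × 0.00521 = 0.0016, or 6.6% of the margin.

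**Losses in the remote arm only.** If *k* of 738 remote participants scoring *s* below the rest are left out, the remote mean rises by (*k*/738) × *s*. At a true difference of 0.025 the error rate is Φ(bias/SE − 1.96), with SE computed from 738 and 738 − *k*.

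| *k* left out | *s* | Error rate |
|---|---|---|
| 4 | 0.05 to 0.30 | 0.028 to 0.050 |
| 7 | 0.20 | 0.055 |
| 12 | 0.10 | 0.050 |
| 15 | 0.05 to 0.30 | 0.039 to 0.213 |

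**Losses in both arms.** Section 6.2 applies to both. With 12 remote and 6 live left out at *s* = 0.10, the net bias is (12 − 6)/738 × 0.10 = 0.00081. SE = 0.10 × √(1/726 + 1/732) = 0.00524, and Φ(0.00081/0.00524 − 1.96) = 0.036. With equal numbers and equal shortfalls the bias is zero and the rate is 2.5%.

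**Follow-up models.** With 10% missing in each arm and 664 analysed, the bias is 0.10 × (between-arm difference among the missing − that among those seen). Doubling needs (1.960 − 1.645) × 0.00549 = 0.00173, so the two differences must be 0.00173/0.10 = 0.017 apart.

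**What the text supports.**

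- 6.2 permits withdrawal but does not say that scores are dropped.
- 6.1 stops the intervention on connection failure; it neither withdraws the participant nor cancels the post inspection. The one cause peculiar to the remote arm is therefore not, as written, a cause of lost data.
- 7.1 inspects directly after the installation in both arms, so for Aim 2 a withdrawal would have to fall within that single session. Installing the seat badly is the outcome being measured, not non-compliance.
- The descriptive paragraph of 8.3 refers to participants as randomised, and nothing in the section narrows that for the models.

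**The case for a change.** The best case for a change is that non-inferiority trials should fix the analysis set in advance, because the choice can move the result towards the claim. The document does not do so. Analysing everyone with a score and analysing only compliant completers would both be consistent with it, and the randomised-participants wording strictly governs descriptive summaries only. Few losses are needed, the arm is known on site, and the 10% attrition allowance protects precision but not against bias. The document also does not say which state of the seat is scored after a stopped session; if on-site help completed a failed remote installation and it was scored as remote, the arms would look more alike.

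Much of this stands as description. The gap is there, the arithmetic is right, and the 4-month models are more exposed than Aim 2. What does not stand is the step from silence to bias. That step assumes that withdrawn participants are excluded, that they are weak installers, and that they come wholly or mainly from the remote arm. None of these is in the text. That the deciding investigator knows the arm is plausible, but the document does not say so. Section 10 also refers to a published protocol and an IRB protocol for other aspects; neither was available, so only this document can be called silent.

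**Conclusion.** No change is called for. Section 8.3 leaves out an analysis set and a missing-data rule, and 6.2 does not say what becomes of a withdrawn participant's data. These are omissions of detail, and the surrounding text points to the usual reading: participants analysed in their assigned arm, using the scores collected. No rule the plan does state is shown to give a wrong result.

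The possible effect runs from nil (2.5% with equal losses and equal shortfalls) through about 3.6% (12 remote and 6 live at 0.10) to about 5.0% (12 remote only at 0.10). The 21% figure needs 15 remote participants averaging three SDs below the rest and no live losses. All these rates rest on assumed counts and shortfalls, the plan's SD of 0.10, and a true difference exactly at the margin. Writing the rule down would leave N at 1476 and power as stated.

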6.3 LOST TO FOLLOW-UP

A participant will be considered lost to follow-up if they fail to attend scheduled visits and/or are unable to be contacted by the study site staff.

7 STUDY ASSESSMENTS AND PROCEDURES

7.1 STUDY ASSESSMENTS

We will consider two primary outcomes, both derived from inspections of child restraint installations using objective coding sheets: (a) total number of inspection points that are correctly installed, translated into a percentage to account for different points for different (e.g., rear-facing vs forward-facing; seat belt vs LATCH) installations, and (b) dichotomous measure of whether the restraint was installed correctly vs. not correctly. Examples of inspection points include whether tether straps are twisted, whether the seat moves more than 1 inch to the left/right, whether seat belts are routed through the correct belt pathway, and whether the carrying handle is in the correct position.

Both outcomes will be collected at four time points: at baseline prior to any intervention, at post, immediately following the initial installation in both groups, at the start of the follow-up visit following 4 months of no active intervention by the research team, and at follow-up after parent installation without technician assistance.

We also will consider results from a brief knowledge questionnaire, which was adopted from an existing instrument. Secondary and covariate measures considered will include demographic traits of the participant (e.g., gender, race, ethnicity, SES, research site) and restraint (e.g., forward vs rear facing, LATCH vs seat belt installation), attitudes and beliefs about child restraints, perceived efficacy of the interventions, and reported behaviors using restraints.

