8 STATISTICAL CONSIDERATIONS

8.1 STATISTICAL HYPOTHESES

- Primary Endpoint(s):

(a) total number of inspection points that are correctly installed, translated into a percentage to account for different points for different (e.g., rear-facing vs forward-facing; seat belt vs LATCH) installations, and
(b) dichotomous measure of whether the restraint was installed correctly vs. not correctly

- Secondary Efficacy Endpoint(s):

results from a brief knowledge questionnaire

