8.2 SAMPLE SIZE DETERMINATION

To conclude non-inferiority of the interactive remote presence condition with $\geq 80\%$ power, Type I error rate of .025, a non-inferiority margin of 0.025, and assuming a common SD of 0.10 (similar to that observed previously), we propose a sample size of 1476. This estimate conservatively assumes 10% attrition based on a two-sample test of non-inferiority difference in means.

The table below presents statistical power to declare non-inferiority between two means, as defined by the alternative hypothesis, assuming a common standard deviation of 0.10, a Type I error rate of 0.025, a sample size per group of 664, the non-inferiority margin (Δ) specified in the row, and the different combinations of intervention means (μ_1, μ_2) specified by the columns. As long as the difference between the two means is less than the assumed non-inferiority margin, the definition of non-inferiority is met and power can be calculated. However, as can be seen by each row of the table, as the difference in intervention means grows, statistical power will decrease.

To illustrate interpretation of the table, if the mean installation accuracy of in-person instruction is 0.90 and the mean installation accuracy of remote instruction is 0.90 (i.e., the two groups achieve equal accuracy), then 664 persons randomized to each group provides 99.5% power to declare non-inferiority of remote instruction to in-person instruction using a Type I error rate of .025, a non-inferiority margin of 0.025, and a common standard deviation of 0.10. Similarly, if the mean installation accuracy of in-person instruction is 0.90 and the mean installation accuracy of remote instruction is 0.89, the two means are not equal but the difference in means ($0.90 - 0.89 = 0.01$) remains less than the declared non-inferiority margin (0.025). Under this scenario, 664 persons randomized to each group provides 78% power to declare non-

inferiority of remote instruction to in-person instruction using a Type I error rate of .025, a non-inferiority margin of 0.025, and a common standard deviation of 0.10.

Table. Statistical Power assuming 664 persons randomized per group (total N = 1476 with conservatively-estimated 10% attrition).

		Combination of mean accuracy scores for intervention groups				
Δ	$\mu_1 = 0.90$ $\mu_2 = 0.90$	$\mu_1 = 0.90$ $\mu_2 = 0.8975$	$\mu_1 = 0.90$ $\mu_2 = 0.895$	$\mu_1 = 0.90$ $\mu_2 = 0.8925$	$\mu_1 = 0.90$ $\mu_2 = 0.8900$	

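### Two outcomes are called primary, but only percentage accuracy has a hypothesis, margin, model and power; the fully-correct non-inferiority test has no margin, effect scale, model type or power

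*Combined protocol and SAP*

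**What the plan says.** Section 7.1 states: "We will consider two primary outcomes, both derived from inspections of child restraint installations using objective coding sheets". They are (a) the percentage of inspection points that are correct and (b) correct versus not correct. Both are measured at four time points, one of them "at post, immediately following the initial installation in both groups". Section 8.1 lists the same two as primary endpoints, the second being the "dichotomous measure of whether the restraint was installed correctly vs. not correctly". Despite its title, 8.1 states no hypothesis, order or success rule.

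Section 8.2 sizes the trial on one outcome: "This estimate conservatively assumes 10% attrition based on a two-sample test of non-inferiority difference in means". Its inputs are a margin of 0.025, a common SD of 0.10 and a Type I error of 0.025.

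In section 8.3, Aim 2 announces two models: one for accuracy and "the other with the dichotomous outcome of correct (100% correct installation across all components) vs. incorrect installation (<100% correct installation) as the dependent variable". It then writes out the hypothesis for "our primary model, based upon installation accuracy", sets the margin ("We will assume a non-inferiority margin of 0.025 for the primary analysis (see power analysis") and describes an ANCOVA of mean accuracy scores with a normality check. The Aim 2 text closes with a one-sided test at 0.025. Aim 3 applies the Aim 2 strategy to six more outcomes, of which (b) and (d) are dichotomous.

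The only expected fully-correct rate is in Aim 1, for the remote arm: "We expect to find over 90% or greater of restraints are installed correctly in all respects". It feeds no power calculation.

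**The concern.** There are two linked problems.

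- **The sections disagree about what is primary.** Sections 7.1 and 8.1 give two primary outcomes; 8.2 and 8.3 work with one. No section says what to conclude if accuracy meets its margin and fully-correct installation does not, or the reverse.
- **One declared primary test is not defined.** A non-inferiority test needs a margin on a stated scale; without one it has no null hypothesis. A margin in mean-score units and an ANCOVA of mean scores do not by themselves define a test of a yes/no outcome. Risk difference, risk ratio and odds ratio are all open, as is the model.

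On the text as it stands, the margin for the second test could be set after the results are known. A margin set that way cannot support a non-inferiority claim. A reader may also take the stated power to cover both primary outcomes.

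**Working it through.** **Inputs from the plan.** Section 8.2: 664 evaluable per group, total 1476, 10% attrition, SD 0.10, margin 0.025, Type I error 0.025 (one-sided in 8.3, so z = 1.96).

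**Step 1. Reproduce the plan's figures for accuracy.**

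- Sample size: 664/0.90 = 737.8, so 738 per arm and 2 × 738 = 1476, as stated.
- Standard error: 0.10 × √(2/664) = 0.00549.
- Power at equal means: Φ(0.025/0.00549 − 1.96) = 0.995, as stated.
- Power at a 0.01 deficit: Φ(0.015/0.00549 − 1.96) = 0.780, as stated.

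All 15 cells of the power table reproduce to within 0.001. The sizing is sound for the outcome it was built on.

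**Step 2. Power for fully-correct installation.** The plan gives no margin, scale or control rate, so three things are assumed: a risk-difference scale, equal true rates p in both arms, and margins m of 0.025 and 0.05 as examples.

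Power = Φ(m/SE − 1.96), with SE = √(2p(1 − p)/664).

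For p = 0.90, SE = √(0.18/664) = 0.01646. With m = 0.025, Φ(1.518 − 1.96) = 0.329. With m = 0.05, Φ(3.037 − 1.96) = 0.859.

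The last column is the margin that would give 80% power, 2.8016 × SE.

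| Assumed rate, both arms | SE | Power, m = 0.025 | Power, m = 0.05 | Margin for 80% power |
|---|---|---|---|---|
| 0.80 | 0.0220 | 21% | 62% | 0.062 |
| 0.90 | 0.0165 | 33% | 86% | 0.046 |
| 0.95 | 0.0120 | 55% | 99% | 0.034 |
| 0.97 | 0.0094 | 76% | >99.9% | 0.026 |

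If all 738 per arm are evaluable at post, power at rates 0.90, 0.95 and 0.97 is 36%, 60% and 80% for m = 0.025, and 89%, 99% and above 99.9% for m = 0.05. The pattern is the same.

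**Step 3. How often the two results would split.** Accuracy power at equal means is 0.9953. The chance that accuracy passes and the dichotomous test fails is therefore at least 0.9953 minus the dichotomous power, and at most 1 minus that power, whatever their correlation. At p = 0.90 this is 0.666 to 0.671 for m = 0.025, and 0.136 to 0.141 for m = 0.05. The same trial would split in about two cases in three or about one in seven, depending on a number the plan does not give.

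**Step 4. Requiring both outcomes.** Because accuracy almost always passes in these scenarios, power for the pair is close to the dichotomous power. At rates 0.90, 0.95 and 0.97 it is about 33%, 55% and 76% for m = 0.025, and 86%, 98% and 99.5% for m = 0.05.

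**The case against.** **Section 8.3 already ranks the outcomes.** It calls the accuracy model primary and ties the margin to it, and 8.2 sizes on it alone. This stands in part: the outcomes are unordered in 7.1 and 8.1, not throughout. But 8.3 does not say whether the second model is co-primary, alternative or supportive, so the conflict remains.

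**Alpha covers both models.** A reader might infer that the dichotomous test has no alpha either. The documents do not support that. The one-sided 0.025 sentence closes a description that opens with two models and can be read as applying to both. Alpha is not part of the gap.

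**Type I error is not shown to be inflated.** A reader might infer that two primary tests at 0.025 raise the error rate. If either outcome sufficed, the one-sided error would be 0.045, 0.042 or 0.035 at test correlations of 0.5, 0.7 or 0.9. No section says that either suffices, and 8.3's single primary model points the other way. If both were required, the error stays at 0.025. These figures are illustrations only.

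**The power figures depend on chosen inputs.** True: they show sensitivity to the missing margin and are not properties of the plan. The split figures also pair the plan's SD of 0.10 with high fully-correct rates. That is an awkward fit, since with 90% of restraints scoring 100%, a mean of 0.90 would need every other restraint to score 0. If failures scored about 80% of points, the SD would be smaller and accuracy power higher still, so the effect on the split is small.

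**Follow-up power is not established.** Section 2.2 reports 66% with any misuse at 4 months. A reader might take 34% as the fully-correct rate for Aim 3 (b), which would give power of about 16% at a margin of 0.025. That figure comes from one sample of 47 parents, and nothing shows that the same inspection sheet was used. It carries no weight here.

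**Details may sit elsewhere.** Section 10 refers to a published protocol and an IRB protocol. A margin may be there, but this document sets out its own hypotheses, sizing and analyses and should state it.

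**Conclusion.** The point holds. Sections 7.1 and 8.1 conflict with 8.2 and 8.3 on what is primary, and one declared primary non-inferiority test has no margin, effect scale, model type or power. Aim 3 (b) and (d) inherit the gap. This rests on the text alone and needs no assumption.

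The claim of at least 80% power applies to accuracy only. On the assumptions of a risk-difference scale, equal true rates and 664 per group, power for fully-correct installation runs from about 33% (rate 0.90, margin 0.025) to above 99.9% (rate 0.97, margin 0.05). The unstated margin can therefore decide the outcome, which is why it must be fixed before the data are seen. The sample size is not wrong for accuracy, and neither an inflated error rate nor a particular follow-up power is shown.

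**What to change.** **Preferred change.**

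- In 7.1 and 8.1 to 8.3, name percentage accuracy at post as the single primary outcome. This follows 8.3; post is the time point that Aim 3's list leaves to Aim 2.
- Make fully-correct installation at post the key secondary, tested at one-sided 0.025 only if accuracy succeeds.
- Analyse it as a covariate-adjusted risk difference, for example standardised from logistic regression, against a risk-difference margin fixed and justified before the data are seen.
- Use the same scale and model for Aim 3 (b) and (d), and state the margin for each.
- In 8.2, say that the power of at least 80% applies to accuracy only, and print the dichotomous power at the chosen margin over a range of rates, for example 0.80 to 0.97 at post and lower rates at follow-up.

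**If the sponsor keeps both as primary.** Require both to succeed and restate 8.2 with power for the pair, which may be below 80%. With a 0.025 risk-difference margin and 90% in both arms, 80% power for the dichotomous test would need 2261 evaluable per arm. That is 2261/0.90 = 2513 per arm after rounding up, or 5026 in total, against the planned 1476. A wider justified margin would need fewer.

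**Cost.** The preferred change needs rewording, one power table and the real work of justifying a margin. It needs no extra enrolment, because no power target attaches to the key secondary. The downside is that an outcome now called primary moves to second place, and its stated power may look less favourable.
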